7.7 Preparation and labelling of Investigational Medicinal Product

The Oculus Go Virtual Reality glasses will be used as a distraction and not as a medical device. Multiple Medical Technique departments of different hospitals (Maasstad Medical Centre, Catherina Hospital, Zuyderland Medical Centre, Martini Hospital and Onze Lieve Vrouwe Gasthuis) have decided that the use of VR-glasses as a distraction not counts as a medical device. This is decided after e-mail contact with [name] from the METC-Z.

7.8 Drug accountability

Not applicable

8. NON-INVESTIGATIONAL PRODUCT**8.1 Name and description of non-investigational product(s)**

Not applicable

8.2 Summary of findings from non-clinical studies

Not applicable

8.3 Summary of findings from clinical studies

Not applicable

8.4 Summary of known and potential risks and benefits

Not applicable

8.5 Description and justification of route of administration and dosage

Not applicable

8.6 Dosages, dosage modifications and method of administration

Not applicable

8.7 Preparation and labelling of Non-Investigational Medicinal Product

Not applicable

8.8 Drug accountability

Not applicable

9. METHODS**9.1 Study parameters****9.1.1 Main study parameter**

The primary outcome is postoperative pain measured on a numeric rating scale (NRS).

9.1.2 Secondary study parameters

Secondary outcomes will be:

- Pre-operative anxiety (State-Trait Anxiety Inventory (STAI)-6 questionnaire)
- Pain catastrophizing (Pain Catastrophizing Scale questionnaire)
- Difference in anxiety scores pre- and post VR intervention (NRS)
- Analgesic use (daily use of paracetamol, NSAIDs, opioids)
- Length of hospital stay
- Tolerability, feasibility and satisfaction of VR use (questionnaire)
- Preoperative pain score (NRS)

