6. TREATMENT OF SUBJECTS

6.1 Investigational product/treatment

The study population will be randomly divided into the intervention group (VR-group) or the standard care-group.

Intervention group (VR-group):

The participants randomised into this group can choose for an immersive guided relaxation VR experience or an interactive VR experience. We will register which option the patients choose. The options are explained in paragraph 9.3. Pre-operatively when arriving at the pre-operative anesthetic room, the level of anxiety and pain is scored using the numeric rating scale (NRS) (T1a). After this, the VR- group will receive their VR experience of own choice on the pre-operative anesthetic room during 10-15 minutes. Directly after this VR intervention, the level of anxiety and pain is scored from 0-10 (T1b).

Direct postoperatively after arriving on the recovery ward, NRS score and level of anxiety from 0-10 will be scored by the participant (T2). Subsequently, the VR-group will receive the VR experience of own choice during 10 minutes. Before leaving the recovery ward, NRS score and level of anxiety from 0-10 will be measured (T3). Depending on the duration of stay on the recovery ward, an extra VR intervention will be given. If the patient stays for less than 3 hours, there will only be one VR intervention. If this is longer than 3 hours, there will be two interventions. The VR intervention is additional to the standard postoperative care management, the standard pain protocol is explained below.

The VR-intervention will be given using the Oculus Go Virtual Reality glasses with touchpad.

Standard pre-and postoperative management (standard care- group):

The participants randomized into the standard care- group will receive the usual standard pre-and postoperative management. Pre-operatively when arriving at the pre-operative anesthetic room, the level of anxiety and pain is scored from 0-10 (T1a). After 10-15 minutes the level of pain and anxiety is again scored from a scale from 0-10 (T1b). Direct postoperatively after arriving on the recovery ward, measurements like NRS score and level of anxiety from 0-10 will be scored by the participant (T2). Before leaving the recovery ward, NRS score and level of anxiety from 0-10 will be measured (T3).

Standard pain protocol:

1. Preoperative (arrival day-care unit) start with 1000mg paracetamol orally administered.

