2. Postoperative Meloxicam 15mg orally administered, or when oral medication is not possible (due to nausea e.g.) than diclofenac supp 100mg or diclofenac i.v. 75mg.
3. On recovery ward, when necessary depending on pain score (NRS>4): dipidolor 2.5-5mg i.v. and 10-15mg i.m. after consulting the anesthesiologist.
4. Postoperative at home 4dd1000mg paracetamol will be continued, in combination with meloxicam 1dd15mg during 3 days. Also tramadol 50mg with a maximum of 4dd will be prescribed.

Study schedule

T0 = Pre-operative ward on day of surgery (when arriving on ward) before randomisation

1. VR-group = Baseline questionnaire, pre-operative anxiety (STAI-6 questionnaire) and pain catastrophizing scale (PCS)
2. Standard care-group = Baseline questionnaire, pre-operative anxiety (STAI-6 questionnaire) and pain catastrophizing scale (PCS)

T1 = Pre-operative anesthetic room

1. VR-group = before VR intervention: pain score (NRS) and anxiety score (NRS) (T1a)
VR-group = after VR intervention: pain score (NRS) and anxiety score (NRS) (T1b)
2. Standard care-group = pain score (NRS) and anxiety scores (NRS) (T1a)
Standard care-group = pain score (NRS) and anxiety scores (NRS) (T1b)

T2= Directly postoperative on recovery ward

1. VR-group = pain score (NRS) and anxiety score (NRS), after this the VR-intervention
2. Standard care-group = pain score (NRS) and anxiety score (NRS)

T3 = Before leaving the recovery ward

1. VR-group = pain score (NRS) and anxiety score (NRS)
2. Standard care-group = pain score (NRS) and anxiety score (NRS)

Questionnaires:

Baseline questionnaire (see attachment 2)

Baseline questionnaire (see attachment 2)
The baseline questionnaire will collect the following variables; age, BMI, ethnicity, education level, vaginal parity, ASA-classification, medication use, intoxications, chronic pain, surgical history, indication of surgery, type of planned surgery.

Pre-operative anxiety (State-Trait Anxiety Inventory (STAI)-6 questionnaire) (see attachment 3)

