11. STATISTICAL ANALYSIS

The data will be analyzed using the program SPSS (version 22). A Chi-square test will be used to assess categorical variables, and the independent sample T-test will be used for continuous variables in case of normal distribution based on the skewness, kurtosis, and graphical representation (histogram) of the continuous variables. The mean NRS-score with standard deviation will be calculated for pain as well as anxiety in both groups, when the data is normally divided. When the data is not normally divided, then a median with interquartile range will be calculated. For categorical variables, frequency and percentage will be calculated. Depending on the amount of missing values, the missing values will be excluded or imputed. This depends on the amount of missing values.

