11.2 Secondary study parameter(s)

The differences in NRS-scores pre- and postoperative of anxiety in both groups (VR-intervention and standard-care group) will be analyzed using the linear mixed models analysis. The results of the STAI-questionnaire, PCS questionnaire, analgesic use and length of hospital stay will be calculated into means with standard deviation and confidence interval. We want to compare the baseline characteristics and questionnaires (STAI and PCS) to see whether the groups are equally divided. The STAI and PCS questionnaire are continuous variables, we will use the independent sample t-test. The tolerability, feasibility and satisfaction of VR use will be calculated into means and frequencies.

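### The secondary outcome of preoperative pain names no time point, and the only test that reaches it ignores the pre-VR score already collected in both arms

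*Combined protocol and SAP*

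**What the plan says.** Sections 3 and 9.1.2 list "Preoperative pain score (NRS") among the secondary outcomes, without a time point, contrast or summary measure. The corresponding anxiety item in the same list does carry a contrast: "Difference in anxiety scores pre- and post VR intervention (NRS").

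The study schedule in section 9.3 gives two preoperative pain scores. In the VR arm these are "VR-group = before VR intervention: pain score (NRS) and anxiety score (NRS) (T1a") and "VR-group = after VR intervention: pain score (NRS) and anxiety score (NRS) (T1b"). The standard-care arm is scored at the same two points; section 6.1 states "After 10-15 minutes the level of pain and anxiety is again scored from a scale from 0-10 (T1b"). The questionnaires come earlier, at "T0 = Pre-operative ward on day of surgery (when arriving on ward) before randomisation", and no pain NRS is listed there. T1a is therefore taken after randomisation but before the VR session.

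On analysis, section 11.1 applies a linear mixed model to postoperative pain. The NRS model in section 11.2 addresses "The differences in NRS-scores pre- and postoperative of anxiety in both groups", and the rest of 11.2 does not mention preoperative pain. The general rule in section 11 is that "the independent sample T-test will be used for continuous variables in case of normal distribution". For other distributions it gives a median with interquartile range and names no test. T1a pain is not named as a covariate anywhere.

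**The concern.** The label fits two scores with different meanings. T1a precedes the VR session, so the session cannot have affected it. T1b follows the session in one arm and an equal wait in the other, so it can show an effect. With the time point open, the choice could be made after the data are seen, in an open-label trial.

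The test that applies by default also leaves out the most useful covariate available. Each woman has a pain score from 10-15 minutes before T1b. A plain t-test on T1b leaves the differences between women that T1a already explains in the error term.

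At stake is the only randomised comparison of the immediate effect of the preoperative VR session on pain. The VR questionnaire asks about this too, but it evaluates the VR experience and so offers no control comparison.

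**Working it through.** **Inputs from the documents.** 1:1 allocation (9.2) and 30 women per arm (5.4). Type I error 0.05, taken as two-sided because the sidedness is not stated (5.4). Effect 15 mm and SD 20 mm (5.4); both were set for pain after surgery and serve here only as illustration.

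**Assumed.** Equal SDs at T1a and T1b, and a T1a-T1b correlation rho of 0.3 to 0.8. The documents give no correlation and no SD for preoperative pain.

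**The plan's own figure.** No figure is given for preoperative pain. For the primary outcome the plan states 26 per group for power 0.8. The normal approximation gives n = 2 × [20 × (1.960 + 0.842) / 15]² = 27.9, so 28 per arm. Power is 0.77 at 26 per arm and 0.83 at 30. That difference is a separate matter; 30 per arm is used below.

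**If T1a is tested.** VR has no effect on T1a, so the test rejects at the type I error rate. In 4,000 simulated trials per correlation the rejection rate was 4.5% to 5.0%.

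**If T1b is tested without adjustment.** The comparison is valid. Adjusting for T1a multiplies the error variance by 1 − rho², so the share of precision lost without it is rho². The 95% half-width is 1.96 × 20 × √(1 − rho²) × √(2/30).

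| rho (assumed) | precision lost, rho² | half-width, T1b adjusted for T1a |
|---|---|---|
| unadjusted | – | 10.1 mm |
| 0.3 | 9% | 9.7 mm |
| 0.5 | 25% | 8.8 mm |
| 0.7 | 49% | 7.2 mm |
| 0.8 | 64% | 6.1 mm |

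In equivalent size, 30 per arm with adjustment matches 30 / (1 − rho²) per arm without it: 40 at rho 0.5 and about 59 at 0.7.

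**Power, for illustration.** With a 15 mm effect and SD 20 mm, power is 0.83 unadjusted. Adjusted, it is 0.92, 0.98 and 0.998 at rho 0.5, 0.7 and 0.8. Simulation of the adjusted test gave 0.91, 0.98 and 0.997.

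**Scores bunched at zero.** The figures above assume roughly normal scores. A second simulation used whole-number 0-10 scores: a latent normal with SD 2.5, rounded and clipped, with a latent VR effect of 1.5 points.
- Latent mean 1, about 42% of T1a scores zero: at latent correlation 0.5, power was about 52% unadjusted and 59% adjusted.
- Latent mean −1, about 73% zero: power was about 32% unadjusted, against 37%, 43% and 51% adjusted at latent correlations 0.5, 0.7 and 0.8.
- Clipping also lowers the correlation actually observed. With latent mean 1, latent 0.7 and 0.8 became about 0.64 and 0.75.
- With latent mean 1 and latent correlations 0.7 to 0.9, the adjusted test had a type I error of 5.2% to 5.7%.

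The direction of the gain is the same throughout. Its size depends on quantities that the documents do not give.

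**The case against.** The strongest case on the other side is that this is an undefined label on one of seven secondary items. The stated aim concerns the immediate postoperative period, and the secondary objectives in the summary omit preoperative pain. The same list includes the STAI-6 and PCS, which are taken before randomisation and compared to check balance, so preoperative pain may be meant descriptively too. This stands as a limit on importance. It does not explain why T1b is collected after VR in both arms and then given no planned use.

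Three stronger readings are tempting, and the documents do not support them.

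- **A reader might infer that T1a and T1b are pooled.** No section pools or averages them; they are always listed separately. Averaging would halve the expected effect, but that loss cannot be charged to the plan.
- **A reader might infer that an unadjusted test throws away most of the precision.** That needs rho² above one half, so rho above about 0.71. Such a value is plausible for scores 10-15 minutes apart, but the documents do not give it, and many zeros would lower it.
- **A reader might take the power gains as forecasts.** The SD and effect were set for pain after surgery. Preoperative pain may be low: chronic pain unrelated to the gynecological problem is an exclusion criterion, and paracetamol is given on arrival.

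It is also fair that T1a is not a textbook baseline. It is scored after randomisation in an open-label trial, so knowing the allocation could influence it. And ANCOVA is not the only sound method; a suitable mixed model would serve.

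**Conclusion.** The point holds as a free improvement. The outcome has two candidate time points and no analysis of its own. The one test that reaches it is unadjusted and applies only if the data look normal; bunched low scores may well fail that check, and then no test is named.

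The faults of definition depend on no assumption. The size of the gain does: an unadjusted T1b comparison is valid but forgoes rho² of the precision, 25% to 64% for assumed correlations of 0.5 to 0.8, and the benefit shrinks when many scores are zero. Only one secondary outcome is affected. The primary conclusion does not depend on it.

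**What to change.** In sections 3 and 9.1.2, define the outcome as pain NRS at T1b, meaning after the preoperative VR session or after the 10-15 minute wait in standard care.

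In section 11.2, state that T1b pain is compared between the randomised groups by ANCOVA with the same woman's T1a pain as covariate, reported as an adjusted mean difference with 95% CI. A mixed model on T1a and T1b, in line with the other NRS outcomes, is equivalent if it gives both arms a common mean at T1a. Without that constraint, its group-by-time term is a change-score comparison, with variance 2(1 − rho) times that of T1b alone. At rho 0.5 this ratio is 1.0, so nothing is gained. State also what is done if the normality check fails.

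Report T1a descriptively as a pre-VR value, without a test, and note that it is scored after randomisation with the allocation open.

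The cost is about one line in each of the three sections. Both scores are already collected in both arms, so no patients, visits or measurements are added. A rule for a missing T1a score is needed.

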9.1.3 Other study parameters

The following baseline characteristics will be collected pre-operatively; age, BMI, ethnicity, education level, marital status, vaginal parity, ASA-classification, medication use, intoxications, chronic pain, surgical history, indication of surgery, type of planned surgery. When patients do not want to answer certain questions, for example marital status or education level, they are free to answer 'unknown'. It is possible that these characteristics may be of influence of pain experience or the experiences in VR. These can be confounders in the study.

9.2 Randomisation, blinding and treatment allocation

After receiving written informed consent, randomisation will be by the Datamanagement randomisation programme of 'Bureau Wetenschappelijk Onderzoek' Zuyderland Medical Centre. Randomisation will be 1:1 for intervention and the standard care- group. The study will be an open label, non-blinded study.

9.3 Study procedures

Patients who were planned for elective gynecological surgery under spinal anesthesia will be informed about the study during their visit at the outpatient clinic. Eligible patients who fulfill the inclusion criteria will be identified and counselled by the research coordinator or staff of the Zuyderland Medical Centre.

Before entry into the study, the research coordinator and/or the staff will explain to potential participants the aims, methods, reasonably anticipated benefits, and potential hazards of the study. They will be informed that their participation is voluntary and that they may withdraw consent to participate at any time during the study. They will be informed that choosing not to participate will not affect their care. After giving sufficient information, written informed consent must be obtained.

After receiving written informed consent and before randomisation, pre-operatively a baseline questionnaire pre-operative anxiety (STAI-6 questionnaire) and pain catastrophizing scale (PCS) questionnaire (T0) will be filled in pre-operatively on the ward. Subsequently the randomisation procedure will be proceeded.

Intervention (VR-group)

The participant can choose a VR- intervention of own preference. They can choose between an immersive guided relaxation or an interactive VR experience. A total of four scenarios can be chosen;

1. Interactive mini-games, such as a game in which the patient immerses into a 360 environment (e.g. Erasmus Bridge Rotterdam), and is asked to guess the name of this environment
2. Mindfulness exercises, in which the patient immerses into relaxing environments and is guided by a mindfulness coach (i.e. guided audio);
3. 360-videos of either relaxing or stimulating environments
4. Speedreading exercises, in which the participant is challenged to read certain articles at his/her highest possible reading speed (in words per minute).

The VR-glasses will be used following the VR-hygiene protocol (see attachment 1).

The participants in the intervention group will also receive the usual standard pre- and postoperative management including the standard pain protocol.

Standard care- group:

The participants randomised into the standard care- group will receive the usual standard pre-and postoperative management.

Standard pain protocol:

1. Preoperative (arrival day-care unit) start with 1000mg paracetamol orally administered.
2. Postoperative Meloxicam 15mg orally administered, or when oral medication is not possible (due to nausea e.g.) than diclofenac supp 100mg or diclofenac i.v. 75mg.
3. On recovery ward, when necessary depending on pain score (NRS>4): dipidolor 2.5-5mg i.v. and 10-15mg i.m. after consulting the anesthesiologist.
4. Postoperative at home 4dd1000mg paracetamol will be continued, in combination with meloxicam 1dd15mg during 3 days. Also tramadol 50mg with a maximum of 4dd will be prescribed.

Study schedule

T0 = Pre-operative ward on day of surgery (when arriving on ward) before randomisation

1. VR-group = Baseline questionnaire, pre-operative anxiety (STAI-6 questionnaire) and pain catastrophizing scale (PCS)
2. Standard care-group = Baseline questionnaire, pre-operative anxiety (STAI-6 questionnaire) and pain catastrophizing scale (PCS)

T1 = Pre-operative anesthetic room

1. VR-group = before VR intervention: pain score (NRS) and anxiety score (NRS) (T1a)
VR-group = after VR intervention: pain score (NRS) and anxiety score (NRS) (T1b)
2. Standard care-group = pain score (NRS) and anxiety scores (NRS) (T1a)
Standard care-group = pain score (NRS) and anxiety scores (NRS) (T1b)

T2= Directly postoperative on recovery ward

1. VR-group = pain score (NRS) and anxiety score (NRS), after this the VR-intervention
2. Standard care-group = pain score (NRS) and anxiety score (NRS)

T3 = Before leaving the recovery ward

1. VR-group = pain score (NRS) and anxiety score (NRS)
2. Standard care-group = pain score (NRS) and anxiety score (NRS)

Questionnaires:

Baseline questionnaire (see attachment 2)

Baseline questionnaire (see attachment 2)
The baseline questionnaire will collect the following variables; age, BMI, ethnicity, education level, vaginal parity, ASA-classification, medication use, intoxications, chronic pain, surgical history, indication of surgery, type of planned surgery.

Pre-operative anxiety (State-Trait Anxiety Inventory (STAI)-6 questionnaire) (see attachment 3)

The State-Trait Anxiety Inventory-6 questionnaire is a short questionnaire about the feelings of a person in that specific moment [17]. It consists of questions about anxiety, satisfaction and worries. Women were asked to rank on a 4-point scale (0= not at all, 4 = completely) reflecting on the feelings in that specific moment. To calculate the total STAI score, you have to reverse scoring of positive items (calm, relax, content etc) so 1=4 points, 2=3 points, 3=2 points, 4=1points. You can sum all the scores, multiply the total score by 20 and divide this by 6 [17]. The score ranges from 20 to 90 and the higher the score the more anxiety the person experiences. The STAI questionnaire shows the experience of anxiety at baseline.

Pain catastrophizing (Pain Catastrophizing Scale questionnaire) (see attachment 4)

The pain catastrophizing scale (PCS) has been designed to assess three various dimensions of catastrophizing concerning rumination, magnification and helplessness. It consists of 13 statements describing different feelings and thoughts that can be experienced when in pain. Women were asked to rank on a five-point scale (0 = not at all; 4 = all the time) reflecting on a painful experience in the past [18]. The subscales of the PCS can be calculated separately or overall with a maximum total score of 52 [18, 19]. The higher the score, the more catastrophizing thoughts are present. (see attachments for full questionnaire). The PCS shows how people are able to cope with pain and various thoughts.

NRS:

How did you experience the pain after the surgery?

Anxiety:

How frightened were you after surgery?

VR- questionnaire (see attachment 5)

After the surgery, at the medical ward, a questionnaire will be given to evaluate the experience of VR.

Study schedule

	Informed consent	Baseline questionnaire	PCS and STAI	Pain score (NRS)	Anxiety score (NRS)
Outpatient clinic					
Preoperative (T0) 1. VR-group 2. Standard care group					
Preoperative (T1) 1. VR: before VR intervention (T1A) 2. VR: after VR intervention (T1B) 3. Standard care-group (T1A) 4. Standard care-group after 10-15min (T1B)					
Postoperative (T2), after arriving on recovery 1. VR-group 2. Standard care-group					
Postoperative (T3) before leaving recovery 1. VR- group 2. Standard care- group					

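### The pre-VR pain and anxiety scores (T1a) are taken after open-label randomisation, so the starting score of the secondary anxiety-change outcome can be affected by knowing the allocation

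*Combined protocol and SAP*

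**What the plan says.** Section 9.3 defines the first time point as "T0 = Pre-operative ward on day of surgery (when arriving on ward) before randomisation". Its written content is the same in both arms: baseline questionnaire, STAI-6 and PCS. No NRS item is listed. (The marks in the schedule table at the end of 9.3 cannot be read in the copy reviewed, so this rests on the written list.) After T0, 9.3 continues: "Subsequently the randomisation procedure will be proceeded".

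Section 9.2 states: "The study will be an open label, non-blinded study".

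The first NRS scores are listed under T1, in the anaesthetic room: "VR-group = before VR intervention: pain score (NRS) and anxiety score (NRS) (T1a". Section 6.1 describes these scores within each arm, after allocation. On the VR arm it says "The participants randomised into this group can choose for an immersive guided relaxation VR experience or an interactive VR experience"; on standard care it says "After 10-15 minutes the level of pain and anxiety is again scored from a scale from 0-10 (T1b".

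Section 9.1.2 lists as a secondary outcome "Difference in anxiety scores pre- and post VR intervention (NRS". It also lists preoperative NRS pain. Section 11.2 assigns a linear mixed model to "The differences in NRS-scores pre- and postoperative of anxiety in both groups", but does not say which time points are contrasted or how T1a enters the model. It uses the STAI-6 and PCS to check whether the arms are balanced.

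**The concern.** A baseline is protected by randomisation only if allocation cannot influence it. Here the score labelled as preceding VR is a self-rating of anxiety, given shortly before surgery by a woman who may already know whether she will receive the headset. Section 9.3 has the expected benefits explained before consent, and section 12.4 counts less anxiety before and after surgery among them. Looking forward to VR, disappointment at missing it, or unease about the headset could each move T1a differently in the two arms.

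At stake is the preoperative anxiety comparison. If T1a is subtracted from T1b, or used as a covariate, a difference created by disclosure of the allocation can be mistaken for an effect of the VR session, or can hide one. The same applies to NRS pain at T1a. Patients randomised without an earlier NRS score cannot be given one afterwards.

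**Working it through.** The plan states no figure on this point. The check is of the order of events, followed by the algebra of the possible bias.

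**Order of events** (sections 6.1, 9.2, 9.3)

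1. T0, ward: baseline questionnaire, STAI-6, PCS.
2. Randomisation, open label.
3. T1a, anaesthetic room: first NRS pain and anxiety.
4. VR session, or 10-15 minutes of usual care.
5. T1b: NRS pain and anxiety.

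Sections 6.1 and 9.3 agree on this order. Neither says when the patient is told her allocation, and nothing delays it until after step 3.

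**Algebra.** Let s be the between-arm shift in mean T1a caused by knowing the allocation, p the fraction of it still present at T1b (between 0 and 1), and v the effect of the session on T1b.

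- Difference in change (T1b minus T1a): v + ps − s = v − (1 − p)s. The bias for v is −(1 − p)s: the full s in size if p = 0, and zero if p = 1.
- T1b adjusted for T1a, with equal SDs and correlation ρ: v + (p − ρ)s. With p = 0 the bias is −ρs.
- T1b compared between arms without T1a: v + ps. This is the whole effect of assignment by T1b, and the T1a shift does not enter it separately.

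**Illustration of the extreme case.** The documents give no SD or effect for anxiety. Assume SD 2 points, 30 per arm (section 5.4), ρ from 0.5 to 0.7, no VR effect (v = 0) and complete disappearance of the shift by T1b (p = 0).

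- SE of the difference in change = 2 × √(2(1 − ρ)) × √(2/30) = 0.516 (ρ = 0.5) or 0.400 (ρ = 0.7).
- SE of the T1a-adjusted difference = 2 × √(1 − ρ²) × √(2/30) = 0.447 or 0.369.
- Rejection probability at two-sided 5%, for bias b: 1 − Φ(1.96 − |b|/SE) + Φ(−1.96 − |b|/SE).

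| s | Change score | Adjusted for T1a |
|---|---|---|
| 0.5 point | 16% to 24% | 9% to 16% |
| 1.0 point | 49% to 71% | 20% to 48% |

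Persistence reduces the change-score figures. With s = 1.0 and p = 0.5 the bias is (1 − 0.5) × 1.0 = 0.5 point, so the rejection rate falls to the 16% to 24% of the first row. With p = 1 it returns to the nominal 5%.

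**The case against.** The strongest reply is that the harm is conditional. A VR patient still knows her arm at T1b, 10-15 minutes later, and so does a control. Whatever part of the shift lasts cancels in the change score. A reader might infer that any shift in T1a passes in full into the result; that is only the p = 0 limit, and nothing in the documents says the shift vanishes so quickly. This part of the reply stands.

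A reader might also infer that the trial has no anxiety baseline free of allocation knowledge. It has one: the STAI-6, completed at T0. Its different scale rules out subtracting it from an NRS score, but not using it as a covariate. A comparison of T1b alone is likewise unaffected by a shift in T1a.

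It would be tempting to express an assumed anxiety shift as a share of the 15 mm effect in section 5.4. That effect is for postoperative pain, so the ratio would have no basis.

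Two further points are fair. Section 11.2 does not commit to a T1b minus T1a contrast, and the outcome could be read as T2 to T3. That reading does not remove the concern, because T2 also follows randomisation. And T1b, T2 and T3 are themselves unblinded self-reports; moving the baseline does not change that.

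The order of events is not answered by any of this. Nor does the plan contain an analysis rule that avoids relying on T1a.

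**Conclusion.** The point holds for the secondary NRS outcomes. T1a is a post-randomisation, open-label score and can be affected by knowledge of the allocation. The resulting bias in the between-arm difference in change is (1 − p)s in size, hence at most s. Both s and p are unknown, and so is the sign. The rejection rates above show what could happen under stated assumptions; they do not predict what will.

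The conclusion rests on an inference that patients learn their allocation before T1a. That is the natural reading of an open-label trial randomised after T0, but the documents do not state the moment of disclosure.

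A reader might extend the concern to the primary outcome. The documents do not support that: it is postoperative NRS pain, and section 11.1 does not name T1a as its baseline.

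**What to change.** Adopt one of the following and state it in sections 9.3 and 11.2.

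- **Open the allocation only after T1a is recorded.** T1a then becomes a baseline free of allocation knowledge. Cost: the headset must be ready for every patient.
- **Add NRS pain and NRS anxiety to the T0 form, before randomisation.** Compare T1b and later NRS scores between arms with the T0 NRS score as covariate. Keep T1a as a descriptive pre-session score, and do not adjust for it. The T0 score should not replace T1a as the subtracted starting value: a T0-to-T1b change would also include the move from ward to anaesthetic room and the effect of learning the allocation. Cost: two extra 0-10 items on a form already completed at that point.

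If neither is adopted, compare T1b anxiety between arms adjusted for the T0 STAI-6. This needs no new data, only a sentence in 11.2.

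In every case, 11.2 should say which time points the anxiety-change outcome covers (T1a to T1b, T2 to T3, or both) and how the baseline enters the mixed model.
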